Short Title:	Botox Injections for MPD			
Principal Investigator:	[name]			
Study Description:	Double-blind placebo controlled clinical trial with participants receiving			
	either a solution of placebo injected into the masseters and temporalis			
	muscles or a solution of botulinum toxin A for treatment of myofascial			
	pain			
Sample Size:	N = 110			
Enrollment:	This study will enroll 110 subjects and screen up to 175			
Study Population:	Eligible participants will be male and female adults ages 18 – 65 identified			
	as having a myofascial pain diagnosis according to the research diagnostic			
	criteria			
Enrollment Period:	18 months			
Study Design:	The study design will be a double-blind placebo controlled clinical trial.			
	The participants will receive either a solution of placebo (total 4cc			
	unpreserved 0.9% sodium chloride) injected into the masseters and			
	temporalis muscles or a solution of botulinum toxin A (a total of 100 units			
	reconstituted with 4cc unpreserved 0.9% sodium chloride). The patients			
	will be stratified into gender groups. The participants will be monitored			
	for 3 months. The primary outcome measure will be pain measured on a			
	visual analog scale prior to treatment and at one, two, three months			
	post-treatment. Secondary outcome measures performed at the same			
	intervals will be quality of life (short form 36), maximum interincisal			
	opening, and functional status via the jaw functional limitation scale			
Description of Sites/ Facili	ties Enrolling			
Participants:	Weill Cornell Medicine			
	Division of Oral and Maxillofacial Surgery Clinic			
	[name]			
	[name]			
	University of Illinois, College of Dentistry			
	Oral and Maxillofacial Surgery Clinic			
	[name]			
	[name]			
Study Duration:	December 31, 2022			
Participant Duration:	Subjects will participate in one injection visit plus 3 follow-up visits at 1-			
	month, 2-months, and 3-months post-injection for a total of 4 months			
Study Agent/Device Name				
Intervention Description:	The participants will receive either a solution of placebo (total 4cc			
	unpreserved 0.9% sodium chloride) injected into the masseters and			
	temporalis muscles or a solution of botulinum toxin A (total of 100 units			
	reconstituted with 4cc unpreserved 0.9% sodium chloride)			

Primary Objective:	The primary objective will be to compare the pain measured on a visual			
	analog scale prior to treatment and at one, two and three months post-			
	treatment in both the Botox and placebo groups.			
Secondary Objectives:	The secondary objectives will be to compare the quality of life (SF-36),			
	maximum interincisal opening, and functional status via the jaw			
	functional limitation scale in both the Botox and placebo groups.			
Exploratory Objectives:	None			
Endpoints:	The primary endpoint is improvement of pain on a visual analog scale			
	(VAS) between pre-op, 1, 2, and 3 months post-op. The secondary			
	endpoints are function (MIO/jaw limitation scale) and quality of life			
	(SF36)			

1.1 Schema

Prior to Enrollment Total 110 participants: Obtain informed consent. Screen potential participants by inclusion and exclusion criteria; obtain history, document.

Visit 1 Day 0 Perform baseline assessments: Inclusion/exclusion checklist, pre-operative assessment (maximum interincisal opening), jaw functional limitation scale, visual analog scale, and SF-36 questionnaire

Administer study drug.

T

[figure not shown]
Visit 2 1 – Month

Follow-up assessments of study endpoints and safety: Follow-up assessment (maximum interincisal opening), jaw functional limitation scale, visual analog scale, and SF-36 questionnaire

 Ω

Visit 3 2 – Months

Follow-up assessments of study endpoints and safety: Follow-up assessment (maximum interincisal opening), jaw functional limitation scale, visual analog scale, and SF-36 questionnaire

Page # 11

1.2 Study Objectives

1.2.1 Primary Objectives

The primary objective will be to compare the pain measured on a visual analog scale prior to treatment and at one, two and three months post-treatment in both the Botox and placebo groups.

1.2.2 Secondary Objectives

The secondary objectives will be to compare the quality of life (SF-36), maximum interincisal opening, and functional status via the jaw functional limitation scale in both the Botox and placebo groups.

2. Background

2.1 Disease

Myofascial pain is classically used to describe pain experienced in the masticatory muscles and its associated structures (1). It afflicts nearly 10% of Americans (2). There have been many described treatments such as the use of oral appliances, non-steroidal anti-inflammatory medications, physiotherapy, behavioral therapy and counseling, acupuncture, and botulinum toxin injections (2). However, no single treatment has been found to be significantly superior to the others (2).

2.2 Investigational Agent

Botulinum Toxin-A (BTA) inhibits the release of acetylcholine at the neuromuscular junction, thus preventing further muscle contraction, resulting in paralysis of the affected muscles (3). It is reasonable to expect that those with pain associated with the muscles of mastication will have relief with BTA injection. There will be substantial clinical significance if BTA injections are found to reduce myofascial pain, as this has classically been difficult to treat.

2.3 Rationale

Myofascial pain is classically used to describe pain experienced in the masticatory muscles and its associated structures (1). It afflicts nearly 10% of Americans (2). There have been many described treatments such as the use of oral appliances, non-steroidal anti-inflammatory medications, physiotherapy, behavioral therapy and counseling, acupuncture, and botulinum toxin injections (2). However, no single treatment has been found to be significantly superior to another (2).

Botulinum Toxin-A (BTA) inhibits the release of acetylcholine at the neuromuscular junction, thus preventing further muscle contraction, resulting in paralysis of the affected muscles (3). It is reasonable to expect that those with pain associated with the muscles of mastication will have relief with BTA injection. The clinical significance would be substantial if BTA injections are found to reduce myofascial pain as this has classically been difficult to treat. Prior investigations have been conducted to demonstrate the clinical effectiveness of Botulinum Toxin-A (BTA) for reduction in pain associated with myofascial pain disorder (4). However, no double-blinded randomized controlled

clinical trials have been conducted. The existing evidence is suggestive of a reduction in pain from BTA injections, however there has not been a robust demonstration of this in the literature.

A study conducted by Freund et. al. in 1999 studied 15 subjects who were treated with BTA. 150 units of BTA were injected into the masseter and temporalis muscles bilaterally. Subjects were assessed at 2 week intervals for a total of 8 weeks. There was a statistically significant reduction in the visual analogue scale of pain for these patients with a 45% reduction in reported pain level after 8 weeks (1).

Another study by Guarda-Nardini et al. in 2012 examined 30 patients who were randomized to either receive BTA injections or fascial manipulation techniques (5). A 32% reduction in pain level was found for patients who underwent BTA injections. The existing literature demonstrates a benefit from BTA in pain reduction. This should be examined more closely with a double blinded randomized controlled clinical trial. BTA has been previously FDA approved to treat muscle spasticity of the upper limb as well as chronic migraines but it is considered an off-label use for treatment of myofascial pain disorder in the masticatory region.

[name] is a full-time faculty member of the division of oral and maxillofacial surgery at Weill-Cornell Medicine. She practices the full scope of oral and maxillofacial surgery but has developed a special interest in minimally-invasive temporomandibular disorder treatment efforts including arthroscopic joint surgery and intra-muscular botulinum injections into the masticatory region for myofascial pain disorder. She currently has other research efforts in the area of temporomandibular joint disorder. She is collaborating with a scientist, [name], at Columbia University to grow stem cells from the cartilage, synovial tissues, and synovial fluids removed during the arthroscopic and open temporomandibular joint surgery Standard of care treatment for myofascial pain disorder at Weill Cornell/NYP involves the use of muscle relaxants, NSAIDS, warm compresses, night guards, and physical therapy. Botulinum injections into the masticatory muscles is a commonly performed adjudicative procedure for treatment of myofascial pain disorder at Weill-Cornell/NYP.

2.4 Risk/Benefit Assessment

2.4.1 Known Potential Risks

Risks of BTA include side effects such as:

- problems swallowing, speaking, chewing, or breathing due to weakening of associated muscles
- spread of toxin effects causing muscle weakness
- allergic reactions
- discomfort at the injection site
- headaches
- bruising at injection site
- syncope due to anxiety or needle related pain
- muscle atrophy
- facial palsy
- localized numbness
- skin infections

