4.3 Exclusion Criteria

- 1. Baseline pain measured by the subject < 3.5/10 on visual analog scale
- 2. Central/neuropathic pain disorder affecting the masticatory muscles
- 3. Temporomandibular joint arthralgia that is more severe than the myofascial pain disorder affecting the masticatory muscles
- 4. Previous temporomandibular joint surgery
- 5. Systemic arthropathies
- 6. Fibromyalgia
- 7. Allergy to study medications
- 8. Traumatic injury of masticatory muscles or temporomandibular joint within last 12 months
- 9. Mandibular fracture within the last 12 months
- 10. Pregnancy or breastfeeding
- 11. Cervical radiculopathy or surgery
- 12. Prior Botox injection in the masticatory muscles
- 13. Initiation of additional treatment of MPD within the past 3 months

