13.1.1 Investigational Agent or Device Risks (Expected Adverse Events)

Expected risks of BTA include:

- Problems swallowing, speaking, chewing or breathing due to weakening of associated muscles
- Spread of toxin effects causing muscle weakness
- Allergic reactions
- Discomfort at the injection site
- Syncope due to anxiety or needle related pain
- Muscle atrophy
- Facial palsy
- Localized numbness
- Skin infections

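### The eligibility criteria do not address pre-existing impairment of neuromuscular transmission, swallowing or breathing, although the protocol's own mechanism and risk lists point to these functions

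*Combined protocol and SAP*

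**What the plan says.** On mechanism, section 2.2 states that BTA "inhibits the release of acetylcholine at the neuromuscular junction, thus preventing further muscle contraction, resulting in paralysis of the affected muscles". Sections 2.3 and 3.2 repeat this.

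On risk, section 2.4.1 opens its list with "problems swallowing, speaking, chewing, or breathing due to weakening of associated muscles", followed by "spread of toxin effects causing muscle weakness". Section 13.1.1 carries the first item over as an expected adverse event ("Problems swallowing, speaking, chewing or breathing due to weakening of associated muscles"), and section 14 lists both as anticipated.

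On eligibility, section 4.2 has 4 inclusion criteria: age, capacity to consent, an RDC/TMD diagnosis and a minimum baseline pain score. Section 4.3 has 13 exclusions. One of them corresponds directly to a listed risk: "Allergy to study medications". The two others that come nearest to the subject are "Central/neuropathic pain disorder affecting the masticatory muscles" and "Cervical radiculopathy or surgery".

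On handling the risks, section 2.4.3 provides for telling participants about them before consent. Section 14 provides for monitoring adverse events after treatment.

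**The concern.** The protocol identifies the functions that the drug can weaken, and then leaves eligibility silent on people in whom those functions are already weak. It does screen for allergy, the third item in each risk list, but does not explain why the first two items have no counterpart among the criteria.

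Participant protection is at stake. Treatment is given once, so eligibility is the main written point at which exposure can be prevented. If the criteria are silent, whether such a person is injected depends on the judgement of whoever sees them, at two sites. Section 4.6 invites referrals from neurologists and otolaryngologists and adds recruitment through social media and fliers, so it is plausible that such a person could come forward.

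**Working it through.** The plan gives no figure on this point, so the check is a comparison of texts: every criterion against the listed functions, then a search for any other provision that does the same job.

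**Step 1: the criteria.**

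| Criteria | Subject | Addresses neuromuscular transmission, swallowing or breathing? |
|---|---|---|
| Inclusion 1 to 4 | Age, consent, diagnosis, pain score | No |
| Exclusions 1 to 3 | Pain severity; pain of central, nerve or joint origin | No |
| Exclusions 4, 5, 8, 9 | Joint surgery, arthropathy, trauma, fracture | No |
| Exclusion 6 | Fibromyalgia | No |
| Exclusion 7 | Allergy | No |
| Exclusion 10 | Pregnancy, breastfeeding | No |
| Exclusion 11 | Cervical nerve root or surgery | No |
| Exclusions 12, 13 | Earlier Botox in these muscles; newly started treatment | No |

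Count: 0 of 4 inclusion criteria and 0 of 13 exclusions.

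**Step 2: an example.** Take a 40-year-old who can consent, has an RDC/TMD diagnosis of masticatory myofascial pain, scores 5/10 on the visual analog scale and has known dysphagia. All 4 inclusion criteria are met (5 is above the 3.5 threshold). With nothing else in the history, none of the 13 exclusions applies. The person is eligible as the plan stands and, at the 1:1 ratio in 6.1.1, would have a 1 in 2 chance of BTA if randomised.

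**Step 3: other provisions.**

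- *Disclosure (2.4.3).* It informs the participant but excludes nobody.
- *Medical history.* Table 1 marks it at both the Pre-Study and Treatment visits, and the schema in 1.1 also places a history before enrolment. Section 6.1.1, however, lists only consent, the checklist and the pharmacy order at Pre-Study; 6.1.2 lists history at the Treatment Visit. In neither place is the history tied to a criterion of this kind.
- *Inclusion/exclusion checklist (6.1.1).* Its items are not reproduced. A checklist that follows 4.2 and 4.3 would contain nothing on this.
- *Concomitant medication (7.8).* It is recorded, with no link to eligibility.
- *Withdrawal (8.2).* One ground needs an exclusion criterion that exists. Another lets the investigator withdraw someone for a medical condition that makes continuing contrary to their interest. That is discretionary.
- *No later stop (8.1).* There is one intervention and no discontinuation of it.
- *Monitoring (14).* It detects harm after exposure.

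**Step 4: what is stated and what is inferred.** The mechanism and the risks to swallowing and breathing are stated. That someone with impaired neuromuscular transmission, swallowing or breathing is more exposed to those risks is inferred from the mechanism and from the listed spread of effect. No section says so.

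**The case against.** The strongest reply is that the documents name no susceptible subgroup. The risk lists describe effects in treated people generally, and the order of the bullets is not a ranking by frequency or severity. This stands: the higher exposure is an inference, and the point is worded accordingly.

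A second reply is that other safeguards exist. Randomisation is triggered at the Pre-Study visit and injection follows at a separate visit where history is listed, so 8.2 could be used in between. Entry also follows a consultation with the investigator (4.6). This stands in part. It would be wrong to say that nothing could stop such a person being injected, or that they would certainly be randomised. But 8.2 speaks of a condition that occurs, which fits poorly with one already present at entry, and its use is optional. It is not an eligibility rule.

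A third reply is that some exclusions come close. Prior Botox in the masticatory muscles (exclusion 12) may keep out people whose muscles are already weakened, and exclusion 11 may touch weakness or numbness. Both are fair, so allergy should not be called the only listed risk on which the exclusions act. Neither reaches swallowing, breathing or neuromuscular transmission.

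A reader might also infer that admitting such people would confuse adverse event attribution and distort the mouth-opening and jaw-function results. The documents largely answer this. Section 13.4 treats a condition present at screening as baseline and records only deterioration. Mouth opening and jaw function are measured before injection and compared between randomised arms with repeated measures. A few such participants would not materially bias that comparison.

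Finally, section 8.1 is not itself a fault. With one injection visit, the absence of discontinuation follows from the design. It matters here only because it leaves eligibility as the main point of control.

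**Conclusion.** The gap is real and is one of participant protection. None of the 17 criteria (4 + 13) addresses pre-existing impairment of neuromuscular transmission, swallowing or breathing, while three sections list weakness affecting swallowing and breathing, and spread of effect, as risks. A person with such impairment meets the criteria and could be randomised. The remaining safeguards are disclosure, an unlinked history and discretion.

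The size cannot be put in numbers. The documents give no frequency of such conditions; the assumption is that few of the 110 participants would be affected. The case rests on the harm being foreseeable from the protocol's own text, not on how many people it concerns.

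A reader might infer that the protocol knowingly admits its highest-risk patients, or that each would face a serious event. The documents support neither. They identify no high-risk group and give no event rates. Nor does the gap put the trial's efficacy conclusions in doubt. It should be closed because closing it is simple and the plan gives no reason for leaving it open.

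**What to change.** The sponsor and clinical investigators should reconcile section 4.3 and the inclusion/exclusion checklist in 6.1.1 with the risks in 2.4.1, 13.1.1 and 14, so that pre-existing impairment of the functions named there is addressed at screening. They should decide the clinical content, including which conditions and what degree of impairment matter, and word it so that both sites apply it alike. If they conclude that no criterion is needed, the protocol should give the reason.

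Timing matters. The answer should come from the history already collected and be complete before the pharmacy order triggers randomisation. Section 6.1.1 should therefore list the history that Table 1 already marks at Pre-Study.

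The cost is a criterion, a checklist line and a protocol amendment, with no new procedure. Some eligible patients would be lost, probably few, but the number is unknown. The plan allows up to 175 screened for 110 enrolled, which leaves 175 − 110 = 65 for screen failures of every kind, and it gives no expected failure rate against which to judge a further exclusion. The inputs to the power calculation in 12.1 (55 per arm, a difference of 1.0, a standard deviation of 1.5) do not change.

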2.4.2 Known Potential Benefits

Possible direct benefits of participating in the study are a decrease in pain level, increase in range of motion of the jaw (mouth opening), or improved jaw function. Possible indirect benefits of participating in the study are improvement of quality of life by decrease in pain and improved jaw function. Participants may have increased ability to eat and speak without pain or limitation in function. Information collected in the study may help benefit others who suffer from myofascial pain disorder. We hope to learn more about the efficacy of BTA in treatment of this disorder.

2.4.3 Assessment of Potential Risks and Benefits

Subjects will be informed of all potential risks and benefits of BTA prior to consent and enrollment on the study so that they can determine whether or not they would like to participate in the study.

2.5 Correlative Studies Background

Not Applicable

3. Study Design

3.1 Overall Design

for three months.

The proposed study is a randomized clinical trial comparing BTA to placebo injections into the masseter and temporalis muscles in management of myofascial pain disorder. The hypothesis is that injections of BTA reduces the intensity of myofascial pain more than placebo. Currently, in the literature, there is no evidence for the best non-surgical treatment modality for treatment of myofascial pain disorder of the muscles of mastication. Many different approaches have been described such as oral appliances, medications (NSAIDS and muscle relaxants), physiotherapy, acupuncture, trigger point injections, and botulinum injections. To date, the literature concerning trigger point injections and botulinum injections for treatment of myofascial pain disorders of the muscles of mastication is limited. Currently, injection of BTA is not FDA approved for myofascial pain disorder of the masseters and temporalis muscles.

Eligible participants in the clinical trial will be male and female adults ages 18 – 65 identified as having a myofascial pain diagnosis according to the research diagnostic criteria. All subjects will have myofascial pain disorder. Healthy controls will not be involved in the study. The study design will be a double-blind placebo controlled clinical trial. The participants will receive either a solution of placebo (total 4cc unpreserved 0.9% sodium chloride) injected into the masseters and temporalis muscles or a solution of botulinum toxin A (total of 100 units reconstituted with 4cc unpreserved 0.9% sodium chloride). Both treatment groups are considered investigative. The patients will be stratified into gender groups. The participants will be monitored

The primary outcome measure will be pain measured on a visual analog scale prior to treatment and at one, two and three months post-treatment. Secondary outcome measures performed at the same intervals will be quality of life (short form 36), maximum interincisal opening, and functional status via the jaw functional limitation scale. The only study procedures are the injection of botulinum toxin or placebo and the use of visual analog scale, measurement of maximum incisal opening and the use of visual analog scale and questionnaires.

On the first visit, participants will be asked to fill out questionnaires. The questionnaires completed on the first visit include health history and history of present symptoms. Participants will then rate their pain on a visual analog scale. The visual analog scale is a 10cm line in which participants are asked to place a hash mark somewhere along that line to represent the amount of pain they feel. The other questionnaires completed on your first visit will be the short form 36 quality of life scale and the jaw functional limitation scale. The participant will then undergo an injection of either botulinum toxin or saline into the masseter and temporalis muscles. The participants are then reevaluated at one, two, and three months post-treatment. They will be asked to fill out the same questionnaires about quality of life and jaw function. They will again rate their pain on the same visual scale. Maximum incisor opening will be measured at these visits.

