12.1 Study Design/Endpoints

Based on the preliminary data and the sample size calculations estimating a difference in mean prepost VAS change between groups of 1 point or greater (on a scale of 1-10), we plan to enroll a total of 110 subjects between the two study sites. Estimated 55 subjects will be enrolled at Weill-Cornell Medical Center/ New York Presbyterian Hospital and 55 subjects will be enrolled at the University of Illinois at Chicago. With 55 patients in the botulinum toxin A injection group and 55 patients in the placebo group (N=110), the study will have more than 90% power to detect a difference in mean in pre-post change between groups of 1.0 point or greater on VAS, using a two-sided t-test and assuming a standard deviation of 1.5 for the mean difference. This calculation allows for 10% attrition rate.

An intent-to-treat design will be followed and all subjects will have scheduled outcome evaluations until the end of the study, death of the subject, or subject refusal. Subjects will be withdrawn from their randomly assigned treatment for considerations of subject safety only. Descriptive statistics including mean, standard deviation, median, range, frequency, and percent will be calculated for the entire cohort as well as by the study arm (botulinum toxin A and unpreserved 0.9% sodium chloride) to assess the results of randomization and identify potential confounders.

The primary analyses of the data will be performed according to subjects' original treatment assignment (i.e., intention-to-treat analyses) and the inclusion of all data from all subjects randomized in the final analysis. To assess the primary endpoint of improvement of pain on a visual analog scale (VAS) between pre-op, 1, 2, and 3 months post-op, a repeated measure of analysis of variance will be performed with one between subject factor (botulinum toxin A versus placebo) and one within subject factor (time). This analysis will also be used for the secondary endpoints: function (MIO/jaw limitation scale) and quality of life (SF12). In the event of significant loss to follow-up, we will explore the use of a linear mixed model to assess the independent effect of the study group on VAS over the study visits. The paired t-test, or the signed-rank test as appropriate, will be used to assess change in pain, function, and QOL between pairs of relevant time points for both study arms.

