12.3 Stratification Factors

Not applicable

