12.4 Analysis of Endpoints

12.4.1 Analysis of Primary Endpoints

To assess the primary endpoint of improvement of pain on a visual analog scale (VAS) between pre-op, 1, 2, and 3 months post-op, a repeated measure of analysis of variance will be performed with one between subject factor (botulinum toxin A versus placebo) and one within subject factor (time). In the event of significant loss to follow-up, we will explore the use of a linear mixed model to assess the independent effect of the study group on VAS over the study visits.

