12.4.2 Analysis of Secondary Endpoints

The same analysis as that of the primary endpoints will also be used for the secondary endpoints: function (MIO/jaw limitation scale) and quality of life (SF36).

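### The synopsis and 3.1 say patients are stratified by gender, 12.3 says stratification does not apply, and the section 12 models leave gender out

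*Combined protocol and SAP*

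**What the plan says.** Two design statements name gender. Section 3.1 says "The patients will be stratified into gender groups", and the Study Design entry of the synopsis says patients "will be stratified into gender groups". Neither says whether allocation, analysis or both is meant.

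The statistical section says otherwise. Under "12.3 Stratification Factors" the whole entry is "Not applicable". In 12.1 the descriptive statistics "will be calculated for the entire cohort as well as by the study arm", with no breakdown by gender. The primary model in 12.1 has "one between subject factor (botulinum toxin A versus placebo") and time as its within-subject factor, and 12.4.1 repeats it. For the secondary endpoints, 12.4.2 states: "The same analysis as that of the primary endpoints will also be used for the secondary endpoints". Section 12 has no gender term, subgroup or interaction.

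Sections 6.1.1 and 7.11 give 1:1 allocation and say who developed and holds the randomisation scheme. They name no strata and no blocks.

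**The concern.** Whether randomisation was stratified, and by what, is a basic design fact, and a reader of this document cannot state it. It also bears on the analysis. If allocation was stratified and balanced on a factor that predicts the outcome, a model without that factor leaves the factor's variance in the error term although the design has removed it from the treatment contrast. Standard errors are then too large, intervals too wide and p-values too high. If nobody settles the matter until after unblinding, whether to adjust for sex becomes a discretionary choice made with the results in view.

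**Working it through.** **1. The statements side by side, on each meaning of stratified.**

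| Meaning | Against 12.3 | Against the models and summaries in section 12 |
|---|---|---|
| Allocation by gender | Direct contradiction | The stratum is not in any model |
| Results broken down by gender | No necessary conflict, if 12.3 concerns randomisation strata | The breakdown is not specified |
| Neither (12.3 is right) | The synopsis and 3.1 are wrong | Section 12 is consistent with itself |

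**2. The plan's own power.** Inputs from 12.1: 55 per arm, difference 1.0 VAS point, SD 1.5, two-sided t-test, 10% attrition; alpha 0.05 is also from section 12. Completers: 55 × 0.9 = 49.5 per arm. Noncentral-t power is 93.4% at 55 per arm and 90.7% at 49.5. The stated figure of more than 90% is reproduced, and no gender input enters it.

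**3. Effect of leaving a stratum out.** Let R² be the share of variance in VAS change explained by sex. The documents do not give it, so a range is assumed. This step also assumes allocation stratified by sex and balanced within sex. For a change-score comparison, by normal approximation:

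- True alpha = 2Φ(−1.96/√(1−R²)).
- Interval width factor = 1/√(1−R²).
- SE = 1.5 × √(2/49.5) = 0.3015, so the planned half-width is 1.96 × 0.3015 = 0.591.
- Unadjusted power = Φ((1/0.3015 − 1.96)/√(1−R²)).
- Adjusted power = Φ(1/(0.3015 × √(1−R²)) − 1.96).

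| R² | True alpha | Interval too wide by | Correct half-width | Power unadjusted | Power adjusted |
|---|---|---|---|---|---|
| 0 | 0.050 | 0% | 0.591 | 0.9126 | 0.9126 |
| 0.01 | 0.049 | 0.5% | 0.588 | 0.9136 | 0.9152 |
| 0.05 | 0.044 | 2.6% | 0.576 | 0.9180 | 0.9255 |
| 0.10 | 0.039 | 5.4% | 0.561 | 0.9236 | 0.9377 |
| 0.20 | 0.028 | 11.8% | 0.529 | 0.9353 | 0.9598 |

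Power forgone at R² = 0.05 is 0.9255 − 0.9180 = 0.0075, under 1 point. At 0.20 it is 0.9598 − 0.9353 = 0.0245.

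**4. The planned test.** The table is for a change-score t-test, whereas the plan is a repeated-measures analysis of variance. In simulation (four visits, 98 patients, blocks of 4 within sex, 10,000 null trials per cell), the group-by-time F test without sex has alpha of about 0.04 to 0.05 at R² = 0.05 and about 0.03 at R² = 0.20. The between-subject group test is also about 0.03 at R² = 0.20.

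**5. How plausible is the range?** The sex difference in mean change needed for a given R² is 1.5 × √(R²/(p(1−p))), with p the share of women (assumed). R² = 0.05 needs 0.67 points at a 50/50 mix and 0.84 at 80/20. R² = 0.20 needs 1.34 to 1.68 points, more than the treatment difference the trial is designed to detect.

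**6. When balance is absent.** With simple randomisation within sex, or blocks not stratified by sex, simulated alpha for the unadjusted change-score test is 0.046 to 0.053 throughout. The conservatism disappears, and adjusting for sex is only an optional gain in precision.

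**The case against.** The strongest reply is that section 12 agrees with itself: no strata and no gender term. If 12.3 is correct, omitting gender from the models is no error, and all that remains is a stray sentence in two places. That stands. The contradiction and the missing model term are therefore not two independent defects; the second exists only if the synopsis and 3.1 are right.

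It can also be said that 12.1 intends the descriptive statistics to check the randomisation and look for confounders, and that demographics are collected, so a gender imbalance would probably be noticed. That is fair, but the wording is generic, does not name gender and does not say how patients were allocated. The scheme itself sits with biostatistics and the pharmacy, outside these documents, and silence about strata in 6.1.1 and 7.11 is not a further conflict.

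A reader might infer that 12.3 is contradicted whatever stratified means. It is not: a descriptive breakdown by gender can coexist with having no randomisation strata. A reader might also infer that the randomisation was faulty, the treatment estimate biased or the trial underpowered. The documents support none of these. They show a conflict of wording, not how patients were allocated, and the power statement is reproduced without any gender input.

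**Conclusion.** The point holds as a minor inconsistency. It is a direct contradiction if the sentence concerns allocation, and an unspecified analysis if it concerns results by gender. The documents do not settle which.

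The numerical effect depends on three conditions together: allocation stratified by sex, balance within sex, and sex predicting VAS change. The documents state neither of the last two. Where all three hold, the planned analysis errs towards caution by the amounts shown, all resting on an assumed R² whose upper end is extreme. N = 110 and power above 90% are unaffected.

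It would go too far to say that false positives cannot increase on any reading. If gender groups meant separate tests in men and in women, each at 0.05, the chance of at least one false positive with no true effect would be 1 − 0.95² = 0.0975. The documents plan no such tests, so this is a reason to specify the gender analysis and not a fault already present.

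**What to change.** Make the synopsis, 3.1 and 12.3 agree with the randomisation list actually used, before unblinding.

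- **If sex was a stratum:** name it in 12.3 and in 6.1.1 or 7.11 (block sizes can stay in the restricted file), and add sex to the models in 12.1, 12.4.1 and 12.4.2. Sections 12.1 and 12.4.1 do not say which term is the primary test, and the form depends on it. If it is the group effect, enter sex as a between-subject term. If it is group-by-time, cross sex with time, because with complete data a main effect alone leaves that test unchanged.
- **If sex was not a stratum and no results by gender were meant:** delete the sentence from the synopsis and 3.1. Adjusting for sex is then optional.
- **If results by gender were meant:** state in section 12 that they are descriptive, or a treatment-by-gender interaction, and not separate tests at the 0.05 level.

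The cost is a few lines of text. In the model, with 99 completers there are 99 − 2 = 97 between-subject error degrees of freedom, of which sex uses 1. Crossed with time, it uses 3 of the 3 × 97 = 291 within-subject degrees of freedom. No new data are needed, provided sex is recorded under Demographics in the schedule of assessments.
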